## **8. Study Intervention Discontinuation and Participant Discontinuation/Withdrawal**

### **8.1 Discontinuation of Study Intervention**

Any irregularity or complication during the surgery being performed will be grounds for discontinuation of the study intervention and withdrawal of the subject from the study. If the laparoscopic surgery has to be converted to an open surgical approach due to medical reasons or technical reasons, the study intervention will be discontinued and the subject withdrawn from the study.

No data will be collected at the time of study intervention discontinuation, and any data previously collected will be excluded from the study analysis and appropriately destroyed.

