### **8.2 Participant Discontinuation/Withdrawal from the Study**

Participants are free to withdraw from participation in the study at any time upon request. An investigator may discontinue or withdraw a participant from the study for the following reasons:

- If any clinical adverse event (AE), laboratory abnormality, or other medical condition or situation occurs such that continued participation in the study would not be in the best interest of the participant

The reason for participant discontinuation or withdrawal from the study will be recorded on the on the intraoperative Case Report Form (CRF) and reflected in the WCMC subject registration site. Subjects who sign the informed consent form but do not receive the study intervention may be replaced. Subjects who sign the informed consent form, and receive the study intervention, and subsequently withdraw, or are withdrawn or discontinued from the study will be replaced.

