**Covariates:**

- Demographics
- Preoperative Diagnosis
- Existing Medical Conditions
- Statin drugs in the last 3 months
- Antibiotics in the last 3 months
- Intra-abdominal pressure
- Anesthetic gases
- Total CO2 volume
- Intraoperative complications

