### **13. Adverse Event Reporting Requirements**

This study will not report specific adverse events, as subjects are undergoing surgery for regular care. Furthermore, the device that will be used to collect and analyze the bowel gases from the abdominal cavity during surgery is not in direct contact with subjects and does add additional physical risk to the subjects. During laparoscopy, the abdominal cavity is being insufflated with carbon dioxide (CO2) gas, and a standard pressure between 12mm -15 mm/Hg is maintained throughout the surgery in the abdominal cavity for visualization through a CO2 insufflation tubing connected with one of the surgical trocars. If the pressure changes, for example, during instrument exchange through the laparoscopic port, the CO2 insufflator automatically starts the CO2 flow, so the pressure could be maintained between 12mm -15 mm/Hg. When a gas sample for the study is collected from the abdominal cavity, the insufflator will simultaneously replace any volume of gas removed with new CO2 gas. Therefore, there is no additional risk to the patient due to the gas sample collection for research during the surgery. All the intraoperative complications, should there be any, would be part of the regular surgical care risk.

However, all intraoperative complications will be collected as part of the study data collection. Also, to ensure safety, the intra-abdominal pressure level will be collected as a data point at the time of sample collection as part of the safety monitoring measure.

Any hydrogen (H2) and methane (CH4) detected by the device at time points when clinically, these gases are not expected to be found in the abdominal cavity, the operating surgeon will be notified.

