### **15. Data and Safety Monitoring Plan (DSMP)**

To ensure the safety of clinical research subjects and protect the validity and integrity of research data, subjects will be well acquainted with the research study prior to signing research informed consent. Further, the subjects will be selected strictly according to the study inclusion and exclusion criteria. The electronic data collected as part of this study will be stored in a password-protected computer, and the paper data will be locked in the locked cabinet in the clinical research office located at K802C. We do not anticipate any adverse events related to this study. However, all intraoperative surgical complications will be collected as part of this study data. We will report unanticipated adverse events to the WCMC IRB and to Sentire Medical Systems.

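### Section 8.1 has readings already taken excluded and destroyed when a subject is withdrawn for an intraoperative event; they should be kept and reported

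*Combined protocol and SAP*

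**What the plan says.** Section 8.1 has two triggers. The first is discretionary in form: "Any irregularity or complication during the surgery being performed will be grounds for discontinuation of the study intervention and withdrawal of the subject". The second is mandatory: "If the laparoscopic surgery has to be converted to an open surgical approach", the intervention stops and the subject is withdrawn. In either case nothing is collected at the point of discontinuation, and "any data previously collected will be excluded from the study analysis and appropriately destroyed".

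Under Section 8.2, subjects who received the intervention and then "are withdrawn or discontinued from the study will be replaced". The same section keeps one trace of the event: "The reason for participant discontinuation or withdrawal from the study will be recorded", on the intraoperative case report form.

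Other sections treat intraoperative events as study data. Section 13 says that "all intraoperative complications will be collected as part of the study data collection", Section 13.1.3 puts them on the data collection forms, and Section 15 repeats that "all intraoperative surgical complications will be collected as part of this study data". The covariate list in Section 12.1 includes "Intraoperative complications". Section 11.2.5 has all study documents and data kept in a secure file, with no exception for withdrawn subjects. Section 7.11 relies on consecutive enrolment of 20 subjects to limit selection bias.

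**The concern.** The rule removes readings because of something that happened during the operation, after those readings were taken. A hydrogen or methane value recorded at exploration or mobilisation does not become invalid because the case is later converted.

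Three kinds of information are exposed:

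- **Readings before the event.** These are ordinary intact-bowel values, which Section 3.2 wants for comparison with the open-bowel values.
- **Readings around an unintended bowel injury.** Such an injury is an intraoperative complication, so it is a ground for withdrawal. It is also the event the device is being developed to detect. In a pilot, one such case, whether the device registered it or missed it, would be among the most informative observations.
- **Open-bowel readings.** A subject withdrawn after the bowel has been opened loses the readings that Section 10.1 counts as a response, and is replaced.

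Intra-abdominal pressure, which Section 13 records at each sample as a safety measure, is also within the scope of the destruction clause. It would be lost in the subjects whose operation ran into trouble. An exclusion from analysis can be reversed later; destruction cannot.

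**Working it through.** The plan gives no figure to reproduce: the 20 subjects in Section 12.2 are a pilot number with no power or dropout input. The check is mainly of the text, followed by a gauge of size.

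**Step 1. Section 8.1 beside the other sections.**

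- *Section 11.2.5.* It keeps all study data; 8.1 destroys some. Both cannot be followed for a withdrawn subject. Section 8.1 is the more specific text and would probably govern, so the practical result is loss.
- *Sections 13, 13.1.3 and 15.* They collect all intraoperative complications. They do not mention gas readings of withdrawn subjects, and 8.2 preserves the reason for withdrawal. The fit is poor, because the event may survive while the readings beside it do not.
- *Section 7.11.* Enrolment stays consecutive under 8.1 and 8.2, but the analysed 20 need not be the first 20 operated on. The safeguard is weakened, not contradicted.

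**Step 2. What one withdrawal costs.**

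- Share of the sample: 1/20 = 5%. Share of a cohort: 1/10 = 10%.
- Noted gas values: 2 gases × 1 to 8 time points reached = 2 to 16, plus the continuous trace if the subject is in Cohort 2.
- Pressure values: one per sample, so 1 to 8.

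**Step 3. How many subjects.** The documents give no rate of withdrawal under 8.1.

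- *Bowel injury only.* Section 2.1 cites 0.1% to 9.2%. Assuming that range applies, the expected number in 20 is 20 × 0.001 = 0.02 to 20 × 0.092 = 1.84. The upper end is probably too high here, since the operations are elective and Section 4.3 excludes perforation emergencies, abscess, peritonitis and fistula.
- *Any withdrawal under 8.1.* Let w be the probability that a subject is actually withdrawn. The expected number withdrawn before 20 are retained is 20w/(1 − w). For assumed w of 2%, 5%, 10% and 20% this is 0.41, 1.05, 2.22 and 5.00. These values show scale only; they are not estimates.

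**Step 4. Direction of any effect on the response in Section 10.1.** Take one subject withdrawn after the bowel was opened.

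- Retained result 20/20 = 100%, exact 95% interval from 0.025^(1/20) = 83.2% to 100%.
- If the withdrawn subject was a non-responder, the full figure is 20/21 = 95.2% (76.2% to 99.9%).
- If a responder, it is 21/21 = 100%, with lower limit 0.025^(1/21) = 83.9%. Only precision was lost.
- If the retained result were 18/20 = 90.0%, the full figure would be 18/21 = 85.7% or 19/21 = 90.5%.

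The retained figure can therefore be too high, unchanged or too low. Nothing in the documents links withdrawal to response.

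**The case against.** The strongest case for the plan is this. It is a 20-subject pilot in which Section 12.4.1 calls all analyses exploratory, and analysing completers with replacement is a legitimate choice in such a study. A complication is only a ground for withdrawal, so a subject whose complication is managed can be kept. The reason for withdrawal is recorded. Section 8.1 is specific and 11.2.5 is general.

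Most of that stands, and it rules out several stronger readings that a reader might infer:

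- *That other sections expressly keep or use withdrawn subjects' gas readings.* None mentions them. Sections 12.4.1 and 12.4.2 specify no covariate analysis.
- *That the complications covariate must be empty, or that 8.1 contradicts the completer definition in Section 3.4.* Both follow only if every complication leads to withdrawal, and 8.1 leaves that open. A converted subject is a non-completer under both sections.
- *That retained unexpected gas readings would lean toward false positives.* This assumes that unexpected gas with no injury found stays in. Irregularity is undefined and might cover such a reading, so the text does not settle it. The plan also has no specificity endpoint.
- *That the detection rate would be inflated.* This needs the withdrawn subjects to be non-responders, which nothing supports.
- *That at least one loss is near certain.* Such a figure needs an event rate that the documents do not give, and withdrawal after every event.

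What the defence does not answer is the destruction. Discretion over withdrawal is not discretion over the data once withdrawal has occurred. Reporting completers as the main set does not require erasing the other readings.

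**Conclusion.** The point holds and the rule should be changed. Once a subject is withdrawn under 8.1, valid readings taken before the event are irretrievably lost on account of the course of the operation, and no other section undoes this. The firm conflict is with the general retention rule in 11.2.5. The tension with the complication-collection statements and with the consecutive-subject safeguard is real but weaker.

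The number of subjects affected is unknown and probably small. Each would be 5% of the sample and 10% of a cohort. The bowel-injury figure of 0.02 to 1.84 subjects rests on applying the background range in Section 2.1 to this population, and the wider range of 0.4 to 5.0 rests on assumed withdrawal probabilities of 2% to 20%. The direction of any bias cannot be determined from the documents. The conclusion depends on none of these rates, since the loss is avoidable and permanent however rarely the rule is used.

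**What to change.** In Section 8.1, replace the exclusion-and-destruction clause with a statement such as: *Readings taken before discontinuation are retained and reported with the reason for withdrawal, even if the subject is replaced under Section 8.2.* Collection still stops at discontinuation, as 8.1 now provides.

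In Section 12.4.1, add time-point summaries for all subjects with a reading, beside those for the 20 completers.

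The cost is a protocol amendment with IRB review (Section 11.2.1), possibly a change to the consent wording on data handling, and one extra set of descriptive summaries. Sample size, surgical procedures and replacement are unchanged. The drawback is that n will vary by time point in the all-subjects summaries, so each needs its own denominator.

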### **8.2 Participant Discontinuation/Withdrawal from the Study**

Participants are free to withdraw from participation in the study at any time upon request. An investigator may discontinue or withdraw a participant from the study for the following reasons:

- If any clinical adverse event (AE), laboratory abnormality, or other medical condition or situation occurs such that continued participation in the study would not be in the best interest of the participant

The reason for participant discontinuation or withdrawal from the study will be recorded on the on the intraoperative Case Report Form (CRF) and reflected in the WCMC subject registration site. Subjects who sign the informed consent form but do not receive the study intervention may be replaced. Subjects who sign the informed consent form, and receive the study intervention, and subsequently withdraw, or are withdrawn or discontinued from the study will be replaced.

### **8.3 Lost to Follow Up**

The participant's role in the study is completed at 30 days during which time all data is collected. The subject are coming regularly up to 30 days postop follow up, so we do not anticipate lost to follow up.

## **9. Correlative/Special Studies**

**Not applicable**

### **9.1 Laboratory Correlative Studies**

- 9.1.1 Title – Laboratory Correlative Study #1**
  - 9.1.1.1 Collection of Specimen(s)**
  - 9.1.1.2 Handling of Specimen(s)**
  - 9.1.1.3 Shipping of Specimen(s) (if multicenter)**
  - 9.1.1.4 Site(s) Performing Correlative Study (if multicenter)**

### **9.2 Special Studies**

- 9.2.1 Title – Special Correlative Study #1**
  - 9.2.1.1 Assessment**
  - 9.2.1.2 Method of Assessment**
  - 9.2.1.3 Timing of Assessment**

## **10. Measurement of Effect**

### **10.1 Response Criteria**

Measurement of gastrointestinal gases (CH4 and/or H2) when the bowel is in an open condition will constitute a positive response for this study.

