**1.1 Schema**

Prior to Enrollment

Total N: Obtain informed consent. Screen potential participants by inclusion and exclusion criteria; obtain history, vital stats (age, gender, height, weight, BMI) document.

Arm 1  
20 participants

Surgery Initiation Time Point

Connect Perf Alert™ to Operative Trocar Port  
Sterile tube/filter assembly to be opened in sterile field and affixed to accessible trocar port via standard leur connection ensuring air-tight seal. Surgeon or OR nurse will hand the other end of the tube to the Perf-Alert™ operator for connection.

Post Insufflation Time Point

Post insufflation but prior to initiation of surgical procedure, initiate **Sample Collection** as follows: 1. Open valve of trocar port to allow abdominal gas to pass through. 2. Open valve at Perf-Alert™ and initiate sample collection by turning on pump – let run for 60 seconds. 3. Close valve of trocar to stop the flow of gas from the abdomen.

Time points For Sample Collection

- 1) Initiation of surgery/laparoscopy start Insufflation
- 2) Abdominal exploration
- 3) Completion of colon mobilization
- 4) Colon transection
- 5) At Colotomy
- 6) At Enterotomy
- 7) Anastomosis completion
- 8) End of surgery- after re-insufflation before closure

End of Surgery Time Point

Prior to conclusion of surgery and removal of trocars, repeat Sample Collection procedure.

Post Operative

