#### 3.2 Scientific Rationale for Study Design

Preliminary investigation of a novel device to detect intraoperative bowel perforation/leak during right laparoscopic colectomy. The study will include a prospective quantitative assessment of intra-abdominal gaseous content during intracorporeal anastomosis procedures to determine the detectability of bowel gas or lack thereof when the bowel is intact and open. All study participants will be subject to the same protocol, and there will be no control group given the nature of the study and desired data. Each subject will be its own control using the baseline measurement as reference. For a phase one preliminary investigation, this design is appropriate because we cannot collect the study samples in a retrospective fashion, and the data from the prospective cohorts will provide the necessary information to test the study hypothesis and answer the research question.

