**Sample Collection Table**

Procedure Stage	Laparoscopy Start Insufflation	Abdominal Exploration	Completion of Colon mobilization	Colon transection	At Colotomy	At Enterotomy	After anastomosis completion	Re-Insufflation Before Closure
Sample #	S1_Baseline	S2	S3*	S4*	S5	S6	S7	S8
Time of collection								
H 2								
CH 4								
CO 2								
CO 2 flow/rate								
Intraabdominal Pressure (mmHg)								
Volume								
Re-Insufflation Y_N								

Anesthetic gases								

\*- Collect sample before smoke evacuation

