### **12. Statistical Considerations**

## 12.1 Study Design/Endpoints

**Research question:** Can detectable levels of bowel gas methane (CH4) and/or hydrogen (H2) be detected in the abdominal cavity when the bowel is open during laparoscopic right colectomy with intracorporeal anastomosis using Perf-Alert™ detection system?

**Research Hypothesis: H1:** Bowel gas, methane (CH4) and/or hydrogen (H2) can be detected in the abdominal cavity when the bowel is open during laparoscopic right colectomy with intracorporeal anastomosis using the Perf-Alert™ detection system.

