### Design

Prospective pilot, single-center, single arm, open label, phase 1 investigator-initiated study to determine device ability to detect bowel gas during laparoscopic right colectomy with intracorporeal anastomosis using Perf-Alert™ gas detection system on 20 subjects into 2 Cohorts.

**Cohort 1:** 10 subjects with measurement of bowel gas at 8 predetermined time points during right laparoscopic colectomy as follow:

- Initiation of surgery/laparoscopy start Insufflation
- 2) Abdominal exploration
- 3) Completion of colon mobilization
- 4) Colon transection
- 5) At Colotomy
- 6) At Enterotomy
- 7) Anastomosis completion
- 8) End of surgery- after re-insufflation before closure

**Cohort 2:** 10 subjects with continuous monitoring of bowel gases through the surgery. The level of H2 and CH4 gases will be noted at the 8 predetermined time points during the continuous monitoring as well.

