**12.4 Analysis of Endpoints**

**12.4.1 Analysis of Primary Endpoints**

The gas sample gas composition will be analyzed automatically by the Perf-Alert™ gas detection system at the 8 different predetermined time points listed in 12.1. The measurements will be recorded in the data collection forms. The maximum value for the particular sample gases – H2 and CH4, will be recorded and included in the descriptive analysis.

Specifically, the presence of Hydrogen (H2) and Methane (CH4) gas measured in ppm or mg/L (parts per million or milligrams per liter (mg/L) at the 8 time points during the surgery will be descriptively assessed. Descriptive statistics (e.g., mean, standard deviation, median, interquartile range, frequency and percent) will be calculated for these parameters. Ninety-five percent confidence intervals will be calculated for all parameters of interest to assess the precision of the obtained estimates. No formal hypothesis testing will be performed in the pilot study. However, pairwise time point comparisons will be evaluated by the paired t-test or Wilcoxon signed-rank test, as appropriate. Due to the small sample size in this pilot study, all analyses will be considered exploratory and hypothesis-generating with no adjustment for multiple comparisons. All p-values will be two-sided with statistical significance evaluated at the 0.05 alpha level. All analyses will be

conducted using SPSS for Windows v.25 (IBM Corp. Released 2016. IBM SPSS Statistics for Windows, Version 24.0. Armonk, NY: IBM Corp).

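### The positive-response rule in Section 10.1 omits the own-baseline reference set in Section 3.2, and Section 12.4.1 never computes the either-gas response per subject, with the bowel open or intact

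*Combined protocol and SAP*

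**What the plan says.** Section 3.2 sets out the comparison the study is built on. The aim is "to determine the detectability of bowel gas or lack thereof when the bowel is intact and open", and "Each subject will be its own control using the baseline measurement as reference". The Sample Collection Table in Section 6.1.2 labels S1 as the baseline sample, and the schema in Section 1.1 places the first collection "Post insufflation but prior to initiation of surgical procedure".

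Section 10.1 holds the only definition of response: "Measurement of gastrointestinal gases (CH4 and/or H2) when the bowel is in an open condition will constitute a positive response for this study". It gives no baseline, no margin and no list of the samples that count as open. The hypothesis in Section 12.1 also concerns either gas: "Bowel gas, methane (CH4) and/or hydrogen (H2) can be detected in the abdominal cavity when the bowel is open".

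Section 12.4.1 plans descriptive statistics for H2 and CH4 at each of the 8 time points, including frequency and percent, with 95% confidence intervals. It adds paired t-tests or Wilcoxon signed-rank tests between time points, without saying which pairs matter. It does not mention the response defined in Section 10.1. Section 12.6.2, Evaluation of Response, is marked not applicable.

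**The concern.** Three parts of the plan should connect and do not. Section 3.2 supplies the reference (the subject's own baseline) and the contrast (intact versus open). Section 10.1 supplies a response rule without that reference. Section 12.4.1 supplies an analysis that uses neither the rule nor the open/intact grouping.

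Two things follow. First, if Section 10.1 is applied as written, a background signal already present at S1 and unchanged at S5 or S6 is counted as detection of bowel gas. Second, the quantity most readers will want is the number of subjects in whom the device found either gas once the bowel was open, set beside the number found by the same rule while it was intact. That quantity is not among the planned outputs. If the rule, the samples and the margin are chosen after the data from 20 subjects have been seen, the reported rate can be shaped by those choices.

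**Working it through.** **The plan's own figure.** Section 12.2 gives 10 + 10 = 20 subjects as a pilot number, with no expected rate, precision target or power. The sum is right and there is nothing further to reproduce. All counts below are illustrations; the documents give no readings for this trial.

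**1. Literal rule versus baseline-referenced rule.** Suppose 10 of 20 subjects rise above their own S1 when the bowel is opened, and 2, 4 or 6 others show gas at S1 and the same reading at S5.
- Literal Section 10.1: 12/20 = 60%, 14/20 = 70%, 16/20 = 80% (exact 95% CIs 36.1–80.9%, 45.7–88.1%, 56.3–94.3%).
- Referenced to S1 as in Section 3.2: 10/20 = 50% (27.2–72.8%) in every case.

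If no subject has gas at S1, the two rules agree.

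**2. Can the planned per-gas percentages give the either-gas rate?** For single-gas proportions p and q at one time point, the either-gas proportion lies between max(p, q) and min(1, p + q). With 5/20 for each gas, this is 5/20 = 25% to 10/20 = 50%. If the gases were independent it would be 1 − 0.75² = 43.8%. So the planned table does not determine the rate, even before S5 and S6 are combined within a subject.

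**3. Do the planned pairwise comparisons single out baseline?** Eight time points allow 8 × 7 / 2 = 28 pairs per gas, or 56 for two gases. S1 versus S5 and S1 versus S6, for two gases, are 4 of these. The plan does not say that all 56 will be run. It also does not name these 4. A test on levels does not give a proportion of subjects in any case.

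**4. Why a margin is needed, and why it must suit a difference.** Assume normal errors, independent and equal across readings, and no true gas. If noise pushes a single reading over a limit of k standard deviations 1%, 5% or 10% of the time (k = 2.326, 1.645, 1.282), the difference S5 − S1 has standard deviation √2 and exceeds the same k with probability P(Z > k/√2) = 5.0%, 12.2% or 18.2%.

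At subject level there are two open samples and two gases, with S1 shared within each gas. For margin m, the chance that neither sample exceeds it for one gas is A = ∫ φ(b) Φ(b + m)² db, and the chance that a subject is positive is 1 − A².

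| Single-reading exceedance | Margin m = k | Margin m = k√2 |
|---|---|---|
| 1% | 16.8% | 3.7% |
| 5% | 36.3% | 16.8% |
| 10% | 49.4% | 30.7% |

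Scaling the margin helps but does not remove noise positives. The intact rate therefore has to be read beside the open rate, and on the same number of readings: S5 and S6 for two gases give 4, as do S2 and S3.

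**5. Precision of the proposed outputs.** One cohort at 5/10 has an exact 95% CI of 18.7–81.3%. For a paired example with open 10/20 and intact 2/20 (both 2, open only 8, intact only 0, neither 10), the difference is 40 points. The Newcombe 95% CI is 14.1 to 60.2 with the continuity-corrected correlation, or 16.8 to 58.9 without it.

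**The case against.** The strongest reply is that baseline is already in the study. Section 3.2 sets it for the whole design, S1 is labelled as baseline, and Section 12.4.1 allows S1 to be compared with S5 and S6. Gas presence will be tabulated at all 8 time points with confidence intervals, so S1 to S3, all before colon transection, will stand beside S5 and S6. The names of S5 and S6 describe bowel openings, which leaves mainly S4 uncertain. Section 10.1 sits in a chapter whose other entries are not applicable, as is Section 12.6.2, so a responder analysis may never have been intended. The study is exploratory, and the missing rate could be derived later from data already planned.

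Most of this stands, and it rules out some stronger readings. A reader might infer that the open-bowel result has no comparator at all. The documents do not support that, since per-gas readings before opening will be reported. A reader might also infer that H1 or Section 10.1 itself asks for gas beyond what the subject showed earlier. Neither says so; that idea comes only from Section 3.2. Nor is there a basis for alleging an inflated type I error: Section 12.4.1 disclaims formal hypothesis testing, and no success threshold exists.

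What the reply does not remove is the gap between sections. Section 10.1 states what counts as positive for the study, no analysis uses it, and the planned summaries cannot yield the either-gas rate.

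**Conclusion.** The point holds as a missing link between the design rationale, the response rule and the analysis. It is not a numerical error, and the sample size is unaffected. The response rule should carry the baseline reference, and the analysis should produce the subject-level either-gas rate in both bowel states.

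The size of any effect cannot be known from the documents. It depends on how many subjects have a background signal at S1, and it would be nil if none do. The 60% to 80% against 50% comparison rests on invented counts, and the noise figures rest on independent, equal, normal errors. The 25% to 50% range is a logical bound for 5/20 per gas and needs no assumption about how the gases are related. In a 20-subject descriptive pilot, this is minor to should-fix.

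**What to change.** 1. **Section 10.1.** Define a subject as positive if H2 and/or CH4 at a bowel-open sample (S5 or S6, with S4 as a sensitivity analysis) exceeds that subject's own S1 value by more than a margin set for each gas. The margin should reflect the measurement error of a difference between two readings, come from the manufacturer, and be fixed before analysis.
2. **Section 12.4.1.** Report that proportion with an exact 95% CI, the proportion by the same rule for the intact samples S2 and S3, and the paired difference with a CI. Show these overall and by cohort, because Cohort 1 is sampled at set points while Cohort 2 is monitored continuously.
3. **Sections 12.4.1 and 12.6.2.** Name S1 versus S5 and S6 as the main paired contrast, keep the other pairs descriptive, and make Section 12.6.2 agree.

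**Cost.** Wording in three sections and one figure per gas that the documents do not give. All samples are already collected.

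**Downsides.**
- The headline detection rate may fall.
- Some noise positives remain even with a margin scaled for a difference, so the open rate should not be quoted without the intact rate.
- The table's footnote for S3 and S4 reads "Collect sample before smoke evacuation", so S2 and S3 should also be shown separately.
- The denominator is a completer set, because Sections 8.1 and 8.2 exclude the data of discontinued subjects and replace them. The report should say so.
- Cohort-level intervals will be wide at n = 10.
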